## **4.8 Statistical Evaluation**

### **4.8.1 General Considerations**

Full details of statistical analyses will be described in the Statistical Analysis Plan (SAP), which will be finalized prior to unblinding.

All data will be provided in data listings sorted by treatment group and subject number. Tabular summaries will be presented by treatment group and by visit for all efficacy endpoints. Categorical data will be summarized by the number and percentage of subjects in each category. Continuous variables will be summarized by descriptive statistics, including number of observations, mean, standard deviation, median, minimum, and maximum. Day 1 will be defined as the day of first investigational product administration.

For the purpose of statistical analyses, the data from the placebo-controlled, double-blind period and open-label period will be analyzed separately. Unless otherwise stated, all efficacy analyses will be conducted with a two-sided test at a significance level of  $\alpha = 0.10$ . Nominal p-values will be provided without multiplicity adjustment.

[figure not shown]
Through the end of the double-blind period, missing data for dichotomous endpoints will be handled using the non-responder imputation method, and missing data for continuous endpoints will be handled using mixed effects repeated measures analysis assuming missing at random mechanism.

#### **4.8.2 Sample Size and Power Calculation**

With a total sample size of approximately 342 and a randomization ratio of 2:1:2:2:2, the sample sizes are 76, 38, 76, 76, and 76 for placebo and MEDI2070 low, low-medium, high-medium, and high dose groups, respectively. A 10% dropout rate is assumed for each treatment group in the induction period.

Assuming a placebo CDAI clinical remission rate of 12% and MEDI2070 high dose CDAI clinical remission rate of 31% at Week 8 of the induction period, approximately 76 subjects per treatment group will provide at least 85% power to detect a 19% difference in CDAI clinical remission rates at Week 8 between MEDI2070 high dose versus placebo, using a two-sided test at a significance level of  $\alpha = 0.10$ . The minimum detectable difference in CDAI clinical remission rates at Week 8 will be 11%.

Assuming a 5% placebo SES-CD remission rate and 20% MEDI2070 high dose SES-CD remission rate at Week 16 of the induction period, the given sample size will provide at least 81% power to detect a 15% difference in SES-CD remission rates at Week 16 between MEDI2070 high dose versus placebo using a two-sided test at a significance level of  $\alpha = 0.10$ . The minimum detectable difference in SES-CD remission rates at Week 16 will be 10%.

[REDACTED]

### **4.8.3 Analysis Populations**

Details of each population below and any additional population, if needed, will be described in the SAP.

#### **4.8.3.1 Intent to Treat Population**

The ITT population includes all subjects who are randomized into the study and receive any dose of investigational product for the 28-week, placebo-controlled, double-blind period. Subjects will be analyzed according to their randomized treatment group, regardless of whether subjects receive an investigational product different from that they were randomized to. The ITT population will be used as the primary population for all efficacy analyses. Disposition summary, demographics, baseline characteristics, protocol deviation, and efficacy endpoints will utilize this analysis population.

#### **4.8.3.2 As-treated Population**

The as-treated population includes all subjects who receive any amount of investigational product. Subjects will be analyzed according to the actual treatment received during the placebo-controlled, double-blind period even if it is different from that the subject was randomized to. Analysis of safety endpoints and summary of investigational product administration from the placebo-controlled, double-blind period will utilize this analysis population.

#### **4.8.3.3 Pharmacokinetics Population**

The PK population includes all subjects who receive at least one dose of investigational product and have at least one PK sample containing detectable MEDI2070. The PK population will be used for the PK analysis of the serum PK samples and the evaluation of immunogenicity.

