#### **2.2.2.1 Induction Period**

1. SES-CD remission at Week 16
2. SES-CD response at Week 16
3. PRO2 remission at Week 8
4. PRO2 response at Week 8
5. CDAI clinical response at Week 8
6. Abdominal pain remission at Week 8
7. Abdominal pain response at Week 8
8. Loose/liquid stool frequency remission at Week 8
9. Loose/liquid stool frequency response at Week 8
10. PRO2 remission at Week 16
11. PRO2 response at Week 16
12. CDAI clinical remission at Week 16
13. CDAI clinical response at Week 16
14. Abdominal pain remission at Week 16
15. Abdominal pain response at Week 16
16. Loose/liquid stool frequency remission at Week 16
17. Loose/liquid stool frequency response at Week 16

20. Serum MEDI2070 concentration levels collected during the induction period
21. Incidence of ADA against MEDI2070

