#### **4.8.7 Analysis of Immunogenicity/Pharmacokinetics**

Descriptive statistics of serum MEDI2070 concentration data will be provided by visit. Individual and mean serum concentration-time profiles of MEDI2070 will be generated and included in the report. Pharmacokinetic data obtained in this study will be combined with all available PK data for MEDI2070 and analyzed using population PK methodology. For PK data analysis, time zero is defined as the beginning of infusion.

The presence of ADAs to MEDI2070 in serum will be assessed. Immunogenicity results (binding and, if positive, neutralizing) will be summarized by the number and percentage of subjects who develop detectable ADAs. If possible, the relationship between PK and ADA status will be summarized.

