**Table 3-1 Analysis Populations**

Population	Description
Intent-to-treat (ITT) population	The Intent-to-Treat (ITT) Population includes all subjects who are randomized into the study and receive at least one whole dose of investigational product for the 28-week, double-blind, placebo-controlled treatment period. Subjects will be analysed according to their randomized treatment group, regardless of whether they receive an investigational product that is different from what they were randomized to.
Safety population	The Safety Population includes all subjects who receive at least one dose of investigational product. Subjects will be analyzed according to the actual treatment received during the placebo-controlled, double-blind treatment period even if it is different from what the subject is randomized to.
Open-label population	Open-label population includes all subjects who are enrolled in the open-label treatment period and have at least one dose of open-label MEDI2070 210 mg SC treatment.
PK population	The Pharmacokinetics (PK) Population includes all subjects who receive at least one dose of investigational product and have at least one PK sample containing detectable MEDI2070.

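### Immunogenicity is assigned to a population that requires detectable drug, which excludes placebo from the double-blind ADA evaluation and could drop some treated ADA-positive subjects

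*Combined protocol and SAP*

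**What the plan says.** Protocol section 4.8.3.3 admits dosed subjects to the PK population only if they "have at least one PK sample containing detectable MEDI2070". Its next sentence gives that population two uses: "The PK population will be used for the PK analysis of the serum PK samples and the evaluation of immunogenicity".

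The endpoint concerned is "Incidence of ADA against MEDI2070", a secondary endpoint for induction (protocol 2.2.2.1) that is listed again for maintenance (2.2.2.2). Protocol 4.8.7 says how it is reported: "Immunogenicity results (binding and, if positive, neutralizing) will be summarized by the number and percentage of subjects who develop detectable ADAs". That section names no population, so the denominator of the percentage comes from 4.8.3.3.

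The SAPs do not settle the matter. Both repeat the detectable-drug definition (Table 3.2-1 in the SAP for the full trial, Table 3-1 in the SAP written after early termination), and neither definition mentions immunogenicity. Section 3.10 of the full SAP names the PK population for concentration summaries and names none for ADA. Section 3.9 of the later SAP refers PK and immunogenicity to a separate plan that is not among these documents.

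A population without the drug-detection condition already exists in protocol 4.8.3.2: "The as-treated population includes all subjects who receive any amount of investigational product". It is used for safety endpoints but is not assigned to ADA.

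**The concern.** An ADA rate is a percentage of subjects, so it depends on who is counted. Here entry is decided by a result obtained after dosing, and there are two ways in which that matters.

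First, the condition is tied to treatment assignment. A correctly dosed placebo subject has no MEDI2070 to detect before Week 28. Placebo therefore cannot contribute to the double-blind ADA table, and the active arms have no concurrent post-baseline reference for assay positivity in unexposed subjects. The definition is also not limited to a study period. A placebo subject who completes Week 28, chooses open-label treatment and then has a detectable sample could enter, while one who does not continue could not. Any placebo subjects who got in that way would be a self-selected group of completers.

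Second, the condition can depend on the outcome. Antibodies can speed drug clearance. If drug were never detected in an ADA-positive subject, that subject would leave both numerator and denominator. The PK-by-ADA summary in protocol 4.8.7 would also lose the subjects in whom antibodies had most effect on exposure.

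**Working it through.** **Inputs.** Protocol 4.8.2: "With a total sample size of approximately 342 and a randomization ratio of 2:1:2:2:2", and "the sample sizes are 76, 38, 76, 76, and 76 for placebo and MEDI2070 low, low-medium, high-medium, and high dose groups, respectively". SAP written after early termination, section 1: 29 randomized. The documents visible here give no ADA rate, PK sampling schedule, assay limit or actual arm counts.

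**1. Reproduce the planned arm sizes.** Arm size = 342 × ratio ÷ 9. A ratio of 2 gives 342 × 2/9 = 76, and a ratio of 1 gives 342 × 1/9 = 38. The sum is 76 + 38 + 76 + 76 + 76 = 342, which matches the plan.

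**2. Placebo exclusion.**
- On double-blind samples, 0 of 76 correctly dosed placebo subjects qualify.
- The largest possible double-blind ADA denominator is 38 + 76 + 76 + 76 = 266.
- The share of planned subjects excluded by definition is 76/342 = 22.2%.
- For the 29 randomized, the ratio implies 29 × 2/9 = 6.4 placebo subjects and 29 × 1/9 = 3.2 low-dose subjects.

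**3. What the placebo arm could have shown.** With 0 positives among n placebo subjects, the exact two-sided 95% upper limit for background positivity is 1 − 0.025^(1/n). For n = 76 this is 4.7%. For n = 6 it is 45.9%. The planned arm would have given a useful bound. About 6 subjects give very little.

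**4. Possible loss of treated ADA-positive subjects.** Let N be the treated subjects, x the ADA-positive ones, and e the ADA-positive ones in whom drug is never detected.

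Reported rate = (x − e)/(N − e)

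Reported minus true rate = (x − e)/(N − e) − x/N = −e(N − x)/[N(N − e)]

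This is zero when e = 0 and negative when e > 0 and x < N, so this mechanism can only lower the rate. With N = 266, and with both the true rate and the share lost taken as assumptions:

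| Assumed true rate (x) | 0% of ADA-positive lost | 10% lost | 25% lost | 50% lost |
|---|---|---|---|---|
| 5% (13.3) | 5.0% | 4.5% | 3.8% | 2.6% |
| 10% (26.6) | 10.0% | 9.1% | 7.7% | 5.3% |

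One cell in full, for a true rate of 10% with 25% lost: e = 6.65, and (26.6 − 6.65)/(266 − 6.65) = 19.95/259.35 = 7.7%.

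The 0% column is as consistent with the documents as the others. The table shows direction and possible range and does not estimate what happened.

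**The case against.** The strongest reply is that the governing ADA plan cannot be seen. Protocol 4.8.3 leaves population details to the SAP. Both SAPs drop the immunogenicity clause from the PK population definition, and the later one hands the subject to a separate document. That plan may already use a sensible ADA population. This stands as a limit: it cannot be shown that 4.8.3.3 governed the actual tables. It does not remove the point, because 4.8.3.3 is the only assignment in view and nothing here corrects it. If the separate plan differs, the two conflict and need reconciling.

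A reader might go further and infer that the ADA rate is in fact understated, most of all in the low-dose arm. The documents do not support that. One detectable sample at any time keeps a subject in. Without the sampling schedule and assay limit, neither the existence nor the size of any loss can be shown.

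A reader might also infer that background positivity cannot be assessed at all. That is too strong. Protocol 4.3.6 has ADA samples drawn before dosing, with the schedule redacted. If a Day 1 sample is included, background in drug-naive subjects is visible in the active arms. What is missing is the concurrent post-baseline rate in unexposed subjects. The later SAP also lists all data, so placebo results, if assayed, need not disappear.

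Open-label entry by placebo subjects is likewise only possible, since it requires PK samples after the first open-label dose.

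Finally, the objective is to characterize immunogenicity, no ADA comparison with placebo is planned, and the trial stopped at 29 subjects. These facts limit the consequence. They leave the rule itself unchanged.

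**Conclusion.** The point holds in two parts of different strength. The exclusion of placebo from the double-blind ADA evaluation follows directly from protocol 4.8.3.3, assuming placebo subjects were dosed correctly and the section is applied as written. It affects 76 of 342 planned subjects, and about 6 of 29 randomized by the ratio, with actual counts not given. The loss of treated ADA-positive subjects is a possibility only. It can bias the rate downward by an amount that the documents do not allow anyone to compute, and that may be zero.

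At the size the trial reached, a placebo ADA rate would be very imprecise. Denominators are then so small, however, that one exclusion can change an arm's result: in an assumed arm of 3 with 1 positive, losing that subject turns 1/3 (33.3%) into 0/2 (0%). The rule is worth correcting before ADA results are reported. It has no bearing on the primary efficacy analysis or the sample size.

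**What to change.** - In protocol 4.8.3.3, delete the closing clause that adds immunogenicity to the uses of the PK population.
- In 4.8.7 and in the separate PK and immunogenicity SAP, state that ADA is evaluated in as-treated subjects (called the safety population in the later SAP) with at least one ADA result, by treatment group including placebo. Keep samples taken after the first open-label dose out of the double-blind table.
- Keep the PK population for concentration summaries. In the PK-by-ADA comparison, show separately any ADA-positive subjects without detectable drug, or state that there were none.
- Confirm that the separate SAP uses this same population, and reconcile it with the protocol if it does not.

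This needs a change of wording and no new sampling. If placebo ADA samples were collected but not assayed, there is a small assay cost.

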#### **4.8.3.4 Open-label Population**

The open-label population includes all subjects who are enrolled in the open-label period and receive at least one dose of open-label MEDI2070 210 mg SC. Both efficacy and safety

information from the open-label period will be reported based on this population. Data from the open-label period will be reported by double-blind treatment group and both combined.

#### **4.8.4 Efficacy**

Efficacy data from the placebo-controlled, double-blind period and open-label period will be analyzed separately.

##### **4.8.4.1 Primary Efficacy Analysis**

The primary analysis will be conducted in the ITT population. The primary efficacy endpoint is CDAI remission at Week 8 of the induction period. The primary comparison of interest will be MEDI2070 high dose group versus placebo. The comparisons between MEDI2070 high-medium dose group versus placebo, low-medium dose group versus placebo, and MEDI2070 low dose group versus placebo will also be conducted.

Missing data will be handled using the non-responder imputation method through the end of the placebo-controlled, double-blind period; ie, any subject with missing information on the primary endpoint will be assumed as a non-responder. In addition, subjects with a clinically meaningful increase in steroid use will also be assumed to be non-responders for the primary analysis perspective. Clinical meaningful increase in steroid dose is defined as an increase of at least 5 mg/day for at least 3 days of prednisone, or equivalent, or an increase of at least 3 mg/day for at least 3 days of budesonide.

The difference in CDAI clinical remission rates at Week 8 between MEDI2070 dose groups and placebo group and associated 90% confidence interval will be provided. P-values for comparisons between any MEDI2070 dose group and placebo will be obtained from a logistic regression model adjusting for the number of prior anti-TNF $\alpha$  agents that failed or were not tolerated (1 vs > 1). In the event the number of remissions is too small (ie, < 5), the exact logistic regression will be performed instead. The statistically significant treatment effect will be tested against two-sided alpha level of 0.10.

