## **4.3 Description of Study Procedures**

### **4.3.1 Efficacy**

#### **4.3.1.1 Crohn's Disease Activity Index**

The CDAI is a composite index with weighted domains that quantifies the global disease severity in a single numerical score. It is the oldest and most widely used of several multi-item instruments that have been developed and is validated for use in clinical studies to measure disease activity in CD (Best et al, 1976; Sands and Ooi, 2005). The CDAI measures the severity of active disease using symptom scores that are monitored over the previous week and includes subject-reported symptoms, physician-assessed signs, and laboratory markers. The CDAI score is calculated by summing weighted scores for subjective items (number of liquid or very soft stools, abdominal pain and general well-being) recorded by a diary during a 1-week period, and objective items (associated symptoms, taking antidiarrheal agents such as loperamide/opiates, abdominal mass, hematocrit, daily morning temperature,

and body weight). The CDAI scores range from 0 to 600, with higher scores indicating greater disease activity. Subjects with scores of < 150, 150 to 219, and 220 to 450 represent remission, mild disease, and moderate to severe disease, respectively; whereas subjects with scores of > 450 have very severe disease (Buxton et al, 2007). The CDAI will be calculated at the site in order to determine the eligibility for the study.

The CDAI assessments will be performed at each study visit starting with Visit 2.

[REDACTED]

[REDACTED]

[REDACTED]

[REDACTED]

[REDACTED]

[REDACTED]

[REDACTED]

[REDACTED]

[REDACTED]

[REDACTED]

[REDACTED]

[REDACTED]

[REDACTED]

[REDACTED]	[REDACTED]	[REDACTED]	[REDACTED]	[REDACTED]
[REDACTED]	[REDACTED]	[REDACTED]	[REDACTED]	[REDACTED]
[REDACTED]	[REDACTED]	[REDACTED]	[REDACTED]	[REDACTED]
[REDACTED]	[REDACTED]	[REDACTED]	[REDACTED]	[REDACTED]
[REDACTED]	[REDACTED]	[REDACTED]	[REDACTED]	[REDACTED]

[REDACTED]

[REDACTED]

[REDACTED]

[REDACTED]	[REDACTED]	[REDACTED]	[REDACTED]	[REDACTED]	[REDACTED]	[REDACTED]
[REDACTED]	[REDACTED]	[REDACTED]	[REDACTED]	[REDACTED]	[REDACTED]	[REDACTED]
[REDACTED]	[REDACTED]	[REDACTED]	[REDACTED]	[REDACTED]	[REDACTED]	[REDACTED]
[REDACTED]	[REDACTED]	[REDACTED]	[REDACTED]	[REDACTED]	[REDACTED]	[REDACTED]
[REDACTED]	[REDACTED]	[REDACTED]	[REDACTED]	[REDACTED]	[REDACTED]	[REDACTED]
[REDACTED]	[REDACTED]	[REDACTED]	[REDACTED]	[REDACTED]	[REDACTED]	[REDACTED]

[REDACTED]

[REDACTED]

[REDACTED]

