#### **4.7.2 Prohibited Concomitant Medications**

Subjects must be instructed not to take any medications, including over-the-counter products, without first consulting with the investigator.

The following medications or interventions are considered exclusionary and are not permitted as specified below through Week 52 of the study. The sponsor must be notified if a subject receives any of these during the study:

- Natalizumab (Tysabri®)
- Anti-TNF $\alpha$  agents
- Vedolizumab
- Any commercially available or experimental biologic agent, eg, ustekinumab
- Calcineurin inhibitors eg, cyclosporine (Neoral®) and tacrolimus (FK 506/Prograf®)
- Mycophenolate mofetil (CellCept®)
- Sirolimus (rapamycin)
- IV or intramuscular steroids
- Topical (rectal) aminosalicylic acid (eg, mesalamine) or topical (rectal) steroids
- Thalidomide
- Live attenuated vaccine
- Intra-abdominal surgery
- Elemental diet
- Any experimental product or device as specified in Section 4.1.3 (exclusion criterion #31)

In the event that a subject receives a treatment/intervention listed above, investigational product must be withdrawn and an Early Termination Visit must be completed (see Early Termination visit, Section 4.2.3).

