### 3.3.3 Missing Efficacy Evaluations

Through the end of the DB period (induction and maintenance periods), the missing efficacy data will be handled as described below:

- Missing data for dichotomous endpoints will be handled using the non-responder imputation method, i.e. any subject with missing information on the endpoint will be assumed as a non-responder.
- Missing data for continuous measures will not be imputed.
- Missing data for PRO components (e.g. IBDQ, CD-PRO) will be handled according to the scoring algorithm as described in corresponding sections. If the score is still missing, no further imputation will be done.

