### 3.4 Analysis Visit Windowing Rules

The actual visit for a subject may not exactly coincide with their targeted visit date. The actual visit date will be mapped to the study visit following the analysis visit windowing rules below. Unless specified otherwise, all efficacy and safety analyses will be based on the analysis visits. If there are multiple records fall within the same defined analysis visit window, the non-missing record closest to the target day will be considered for the analysis.

If two non-missing assessment actual dates are equidistant from the target day, the later visit will be considered for analysis.

Composite endpoints (e.g. CDAI score) will be calculated for each date at which individual components are being measured before applying the analysis visit windows rather than to calculate visit window based individual component.

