It was also discovered post-sponsor-transition in Nov 2017 that there was a programming issue where patients that were withdrawn or early terminated could not have follow-up visits recorded in the slate devices. This was due to programming of the slate not allowing for entry of data for any visits post Early Termination visits. The slate was programmed such that follow up visits would only trigger for patients that completed the study at V16 (W12/D85). Therefore, CDAI scores for withdrawn/early terminated patients could not be completed during their follow-up visits. CRF Health provided instructions on 21st Nov 2017 on how sites can record the Early Termination visit as V16, so that follow-up visits could be triggered and CDAI scores calculated. This will include data for any patients with follow up visits going forward from 4th Dec 2017 (date CRAs were provided with new instructions to discuss with sites). A blast email was also sent to all sites with instructions on 19th Dec 2017.

Due to the study closure and timing of LPLV due by 2nd Feb 2018, the CRF Health programming will not be updated. Per the vendor, the slate was programmed incorrectly due to a misunderstanding of the protocol.

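### The non-responder rule sets no date limit or reference dose for steroid increases and gives prohibited rescue no endpoint status, so remission can be misclassified in both directions

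*Combined protocol and SAP*

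**What the plan says.** Two SAPs accompany the protocol: an original SAP for the full design of about 342 subjects, and a final SAP written after early termination with 29 randomized.

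- **Missing data.** Both SAPs (3.3.3) state that "any subject with missing information on the endpoint will be assumed as a non-responder". Protocol 4.8.4.1 says the same for the primary endpoint.
- **Steroids.** Protocol 4.8.4.1 adds that "subjects with a clinically meaningful increase in steroid use will also be assumed to be non-responders for the primary analysis perspective". The threshold is at least 5 mg/day of prednisone or equivalent, or 3 mg/day of budesonide, for at least 3 days. No calendar window or reference dose is given. Original SAP 3.3.3 repeats the clause under a lead-in that runs to the end of the double-blind period (Week 28). Final SAP 3.3.3 omits it.
- **Prohibited therapy.** Protocol 4.7.2 lists biologics, calcineurin inhibitors, rectal therapy, intra-abdominal surgery and others. If one is received, "investigational product must be withdrawn and an Early Termination Visit must be completed". Endpoint status is not mentioned.
- **Later scores.** Protocol 4.3.1.1: "The CDAI assessments will be performed at each study visit starting with Visit 2". The Note to File (final SAP 6.3) gave sites a workaround for early-terminated subjects, "so that follow-up visits could be triggered and CDAI scores calculated". Under 3.4 of both SAPs, visits are mapped by date and "the non-missing record closest to the target day will be considered for the analysis".
- **Data cuts.** The primary analysis follows completion of Week 16 by all subjects and uses everything in the snapshot, including some Week 28 and open-label data. Further analyses follow at Week 28 and study end (protocol synopsis; original SAP 4).

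**The concern.** A Week 8 endpoint should depend on what happened up to Week 8. As written, an increase at Week 12 or Week 20 can make a Week 8 remitter a failure. The same subject could then be a remitter in one data cut and a failure in the next. The missing reference dose adds to this: protocol 4.7.1 directs steroid tapering after Week 16 in subjects with both SES-CD and PRO2 response, so a return to the baseline dose after a taper could be read as an increase and penalise responders.

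The rule is also too narrow. Only missing data and steroid increases make a subject a non-responder. A subject who starts a prohibited biologic, stays in follow-up and has an observed CDAI below 150 in an analysis window is credited to the randomized arm. At stake are the remission rates themselves and whether independent programmers would obtain the same ones.

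**Working it through.** **Inputs.** Protocol 4.8.2: "Assuming a placebo CDAI clinical remission rate of 12% and MEDI2070 high dose CDAI clinical remission rate of 31% at Week 8"; 76 per arm; 10% dropout in each group. Protocol 4.8.1: "all efficacy analyses will be conducted with a two-sided test at a significance level of" 0.10. Rates of steroid increase and of rescue are not given; every such rate below is an assumption.

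**1. The plan's power.** With pooled variance, power = Φ{[Δ − z√(2p̄(1−p̄)/n)] / √[(p₁(1−p₁)+p₂(1−p₂))/n]}. Here Δ = 0.19, p̄ = 0.215, z = 1.645 and n = 76. The numerator is 0.19 − 1.645 × 0.0666 = 0.0804 and the denominator is 0.0648, so power = Φ(1.24) = 0.892. With 76 × 0.9 ≈ 68 per arm it is 0.860; with a continuity correction at n = 76 it is 0.850. The stated figure of at least 85% is reproduced.

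**2. Late steroid reclassification.** If a share f of Week 8 remitters has a later increase, the observed rate is p(1 − f).

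| f placebo / high dose | Rates | Difference | Power, n = 76 | Power, n = 68 |
|---|---|---|---|---|
| 0 / 0 | 12.0% / 31.0% | 19.0 | 0.892 | 0.860 |
| 5% / 5% | 11.4% / 29.45% | 18.05 | 0.874 | 0.839 |
| 10% / 10% | 10.8% / 27.9% | 17.1 | 0.853 | 0.816 |
| 20% / 20% | 9.6% / 24.8% | 15.2 | 0.804 | 0.764 |
| 15% / 5% | 10.2% / 29.45% | 19.25 | not run | not run |
| 30% / 10% | 8.4% / 27.9% | 19.5 | 0.936 | 0.911 |

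The difference widens when 0.12 f(placebo) exceeds 0.31 f(high dose), that is, when the placebo share is more than 31/12 = 2.6 times the high-dose share.

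**3. Rescued subjects counted as remitters.** The result depends on how the rates are expressed.

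- *As a share of all randomized:* bias = (dropout placebo − dropout active) × share rescued × share of those with CDAI < 150. Assuming 15% and 5% dropout, 30–60% rescued and 20–40% below 150, this is 0.10 × (0.3 to 0.6) × (0.2 to 0.4) = 0.6 to 2.4 points of shrinkage. With the plan's own 10% in each arm and equal rescue, it is 0.
- *As a share g of non-remitters:* rate = p + (1 − p)g. Equal g of 5% gives 12 + 88 × 0.05 = 16.4% and 31 + 69 × 0.05 = 34.45%, a difference of 18.05 (power 0.824 at n = 76). At 5% / 2% the rates are 16.4% / 32.38%, a difference of 15.98 (power 0.746).

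These use the Week 8 rates for illustration because the documents state no CDAI rates for Weeks 16 or 28.

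**4. Can a post-rescue score reach a window?** Discontinued subjects are followed for 28 weeks after the last dose (protocol 4.1.6), and the double-blind period can be completed whatever the number of doses (6.3.1). With a last open-label dose at Week 48, the first follow-up at Week 60 is 12 weeks later. But Weeks 60, 70 and 80 are 12, 22 and 32 weeks after Week 48, and span 28 weeks only if counted from Week 52 (8, 18, 28). A last dose at Week 4 would thus give a first follow-up at about Week 16 (12 weeks on) or Week 12 (8 weeks on). The window tables and early-termination section are redacted, so which window it enters cannot be checked.

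**5. Final SAP.** Without the steroid clause, a later increase cannot overturn a remission, but a steroid-rescued subject can count as a remitter. If the planned ratio held (an assumption), a larger arm has 29 × 2/9 ≈ 6.4 subjects, so one misclassified subject moves its rate by 1/6.4 ≈ 16 points.

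**The case against.** *The rule concerns a Week 8 endpoint, so a Week 8 limit is understood.* This is a natural reading. The snapshot text says which data enter the analysis, not that later events redefine Week 8 status. But nothing confines the clause to Week 8, and the only time frame near it in the original SAP ends at Week 28. The text supports that it can be read literally, not that it must be.

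*Rescued subjects will be missing and so fail anyway.* Many will be. The Note to File says follow-up scores for early-terminated subjects could not be recorded until workaround instructions in late 2017, after the decision to close the study. It also shows that those scores were intended, and no readable rule excludes them.

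*Steroid increases are barred (protocol 4.7.1), and escalation for recurrent symptoms stops product (4.1.6).* This limits how often such cases arise. It does not settle how they are scored, since no readable text makes stopping product a non-response.

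*Power stays at or above 85%.* That is so at n = 76 with 5–10% reclassification in both arms (0.874 to 0.853), but not at 68 evaluable (0.839 to 0.816).

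*Scoring rescue as failure is only one estimand choice.* True, but the plan already makes that choice for steroids. Prohibited injected steroids may also fall under the prednisone-equivalent wording; biologics and surgery do not.

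**Conclusion.** The point holds as a defect in a stated rule, with uncertain direction and size. The protocol and original SAP allow a steroid increase after Week 8 to overturn a Week 8 remission. They leave 4.7.2 therapies and surgery without endpoint status, and the final SAP conflicts with the protocol by omitting the steroid clause.

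A reader might go further and infer three things the documents do not support:

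- **That the treatment difference is known to shrink.** Late steroid reclassification can narrow it to 17.1 or widen it to 19.5 under the assumed rates. Rescue bias vanishes if equal shares of each randomized arm are rescued and scored below 150; the 0.6 to 2.4 points require unequal dropout, whereas the plan assumes 10% in every arm.
- **That a follow-up score after a Week 4 last dose is used at Week 16.** The follow-up anchor is unclear and the windows are redacted.
- **That follow-up scores after rescue contaminate the Week 8 endpoint.** On either spacing the first follow-up visit falls after Week 8, so this route matters mainly at Weeks 16 and 28.

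Redacted sections may contain a relevant rule. The final analysis is descriptive, so no test is affected there, but reported remission counts can be.

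**What to change.** In protocol 4.8.4.1 and SAP 3.3.3, state for every dichotomous endpoint at Week X:

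- A subject is a non-responder if, from first dose up to and including that visit, they had the defined steroid increase relative to the baseline dose, received a 4.7.2 prohibited CD therapy, or had CD surgery. Name the 4.7.2 items meant, since the list also contains items that are not CD therapy, such as live vaccines.
- Scores after such an event, including those from early-termination and follow-up visits, do not count as response.
- Events after Week X do not change Week X status.

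Consider also covering new or increased immunomodulators, which 4.7.1 restricts but 4.7.2 does not list. Reconcile protocol 4.8.4.1 with 3.3.3 of both SAPs, and explain the omission if the final SAP means to drop the steroid clause.

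The cost is wording and slightly lower response rates. Concomitant medications are already recorded (protocol 4.7), and time to CD surgery is already a planned summary (4.8.5.1). Partial start dates, which SAP 3.3.1 generally sets to the first of the month, need a stated convention for deciding whether an event precedes Week X. No clinical rule and no sample size changes.
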